8.3.3 Drug accountability

Upon receipt of all IMP, study site personnel or the designated pharmacist will open the shipment package, verify the contents as stated on the enclosed shipping form, and confirm the receipt by filling in and sending the form "Handing over and delivery receipt of Investigational Medicinal Product"

The Investigator will be responsible for documenting the dispensing of the IMP to the patient by entering the unique vial number in the source documents and in the e-CRF.

The amount of administered drug product will be documented by the Investigator in the source documents and in the e-CRF in order to allow drug accountability.

In addition, the sites will maintain paper drug accountability forms to document dispensed IMP per patient. The peel-off labels of the vials will be stuck on these paper drug accountability forms.

inaccessible to any unauthorised individuals.

8.3.4 Destruction of surplus medication

Throughout the study course and at the end of the study, all remaining IMP will be reconciled under the responsibility of the Investigator at the site.

. In case the return is not possible, the

IMP can be destroyed locally, provided that the order for destruction is authorised by the Sponsor.

8.4 TREATMENT ADMINISTRATION- FREQUENCY AND DURATION OF APPLICATION

8.4.1 TLS risk assessment and prophylaxis

At the first "*ramp-up*" dose (Visit 1/Day 1), prior to study drug administration, TLS risk shall be assessed (see *Appendix I: TLS Manual for Investigator* for details) and, during Cycle 1, TLS prophylaxis has to be given prior to each study drug administration, as detailed in the TLS Manual for Investigator.

8.4.2 Premedication

On the first day of each *"ramp-up"* administration visit (i.e. Visits 1 and 8/Days 1 and 8), as well as on each "one shot" administration visit, premedication shall consist of:

- Dexamethasone 8 mg (os or IV) at 12 hours prior to the start of infusion
- Dexamethasone 8 mg (os or IV) to be repeated at 3 hours prior to the start of infusion
- Methylprednisolone 100 mg IV at 1-2 h prior to the start of infusion
- An antihistaminic and an antipyretic agent at 30 to 60 minutes prior to the start of infusion

On the second and the third day of each *"ramp-up"* administration visit (Visit 2, 3, 9 and 10/Day 2, 3, 9 and 10), premedication shall consist of:

- Methylprednisolone 100 mg IV at 1-2 h prior to the start of infusion
- An antihistaminic and an antipyretic agent at 30 to 60 minutes prior to the start of infusion

In case the "ramp-up" administration visit is stopped due to infusion-related toxicities:

- If *"ramp-up"* is resumed after ≥2 days, the premedication at *"ramp-up"* resumption should follow the whole scheme above, i.e. with dexamethasone on the day of *"ramp-up"* resumption and without dexamethasone on the following *"ramp-up"* day(s), if any.
- If *"ramp-up"* is resumed the day after the interruption, premedication without dexamethasone should be given on the day of *"ramp-up"* resumption and on the following *"ramp-up"* day(s), if any.
- If *"ramp-up"* is resumed on the same day of interruption, no additional premedication is needed at *"ramp-up"* resumption.

8.4.3 Step 1 Dose escalation method and cohort management

MEN1112 doses are to be administered to cohorts of 3 patients each. If no Dose-Limiting Toxicity (DLT) is observed in a cohort of three patients at a given dose level, the next cohort of 3 new patients

will be treated with the next higher dose. If a DLT is experienced by one of the three patients at any dose, three additional patients will be treated at the same dose level.

If two or more patients at a given dose level exhibit DLTs, this dose will be defined as the MAD. The MTD is defined as one dose level below the MAD, i.e. one dose level below the one at which ≥ 2 DLTs out of 6 treated patients occur.

In protocol versions from 1.0 to 4.1 n=3 Dose Limiting Toxicity (DLT) evaluable patients per cohort (expanded to n=6 DLT evaluable patients in case of DLT occurrence, with the exception of cohort 0.3 mg/kg which was expanded to n=6 DLT evaluable patients regardless of DLT occurrence) were treated with MEN1112 at escalating doses of 0.1, 0.3, 0.6, 1.0, 1.7, and 2.5 mg/kg using "*one-shot*" infusions.

Starting from protocol version 6.1/6.2, n=3 Dose Limiting Toxicity (DLT) evaluable patients per cohort (expanded to n=6 DLT evaluable patients in case of DLT occurrence) will be treated with MEN1112 at escalating doses of 1.7, 2.0, 3.0, 5.0 mg/kg per each dose cohort using a modified schedule of administration that will include a *"ramp-up"* approach at Cycle 1. Additional intermediate dose levels may be explored, under a 3+3 design, upon recommendation of the independent Data Safety Monitoring Board (iDSMB) that will be appointed to guide dose escalation decisions in place of the Cohort Review Committee (CRC) that was appointed for this role up to Protocol Version 4.1.

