8.4.3.1 Dose-level escalation assessment

In place of the Cohort Review Committee (CRC), which was appointed to guide dose escalation decisions up to Protocol Version 4.1, starting from Protocol Version 6.1/6.2, the decision as to whether, or how, to proceed through the dose levels during Step 1 are guided by the iDMSB which will be comprised of independent AML experts.

The iDSMB will meet by telephone to review the latest safety, PK and Pharmacodynamics (PD) (if any) data prior to dose-escalation to a subsequent cohort, and at any time if needed. Appropriate representatives of the Sponsor and the coordinating CRO will also attend and minute the meeting. Decisions of the iDMSB will be documented and sent to the sites.

The iDSMB is empowered to:

• Review the safety data from the first cycle of each cohort during the dose escalation phase of the study and make dose-escalation (or de-escalation) decisions according to the protocol or making adjustments, as needed. AEs occurring in Cycle 2 which meet the definition of a DLT or are considered clinically significant may also be considered in making dose escalation decisions.

- Consider other AEs, or possible trends in AEs, during the dose escalation phase which may provide relevant information for the dose escalation.
- Confirm the MTD or the maximum dose judged to be tolerable for evaluation in Step 2.
- Review safety data for additional patients recruited at the MTD or the maximum dose judged to be tolerable (at least every 2 months).
- Recommend future dose level and dose schedule administration during the study conduct; advise on premedication, concomitant medication and on any individual patient dose adjustments.

Roles and responsibilities of iDSMB as well as meeting schedule and format of information will be set forth in a separate iDSMB Charter prior to start administrating the drug to the first patient under protocol version 6.1/6.2.

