8.5.4 Pharmacokinetic and Safety Endpoints

8.5.4.1 **Primary Endpoints**

- Identification of **DLT** defined as an adverse event occurring during the first treatment cycle, judged to be related to MEN1112 and meeting any of the following criteria:
 - Grade 3 non-haematological toxicity lasting more than 7 days
 - Grade \geq 4 non-haematological toxicity.

Note: Common complications of AML (in particular infections, bleedings, fatigue) will not contribute to DLT assessment.

• Identification of **MTD** defined as one dose level below the Maximum Administered Dose (i.e. one dose level below the one at which ≥ 2 DLTs out of 6 treated patients occur).

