9. STATISTICAL METHODS AND DETERMINATION OF SAMPLE SIZE

9.1 **DETERMINATION OF SAMPLE SIZE**

Due to the nature of the study, no formal sample size calculation is applicable.

Starting from protocol version 6.1/6.2, up to approximately 6 DLT evaluable patients per dose level will be treated with MEN1112 during the dose escalation phase, while up to approximately 30 patients will be treated in the cohort expansion phase. Considering that the patients no-DLT evaluable during the dose escalation phase will be replaced, and assuming a drop-out rate of 30%, up to approximately 60 patients will be treated with MEN1112. This number might be higher in case additional intermediate dose levels will be investigated.

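### No minimum number of evaluable patients is set at the MTD itself, so it can rest on 0 DLTs in 3 before up to about 30 Step 2 patients are treated there

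*Combined protocol and SAP*

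**What the plan says.** **Escalation (8.4.3).** The next dose opens "If no Dose-Limiting Toxicity (DLT) is observed in a cohort of three patients at a given dose level". One DLT among three adds three patients at the same level. For the ramp-up schedule, cohorts of three evaluable patients are "expanded to n=6 DLT evaluable patients in case of DLT occurrence) will be treated with MEN1112", over "escalating doses of 1.7, 2.0, 3.0, 5.0 mg/kg per each dose cohort".

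**MAD and MTD (8.4.3; primary endpoint in 8.5.4.1 and the synopsis).** "If two or more patients at a given dose level exhibit DLTs, this dose will be defined as the MAD", and then "The MTD is defined as one dose level below the MAD". The primary endpoint words it as "one dose level below the one at which ≥ 2 DLTs out of 6 treated patients occur". The six patients in that phrase are counted at the level above the MTD, not at the MTD.

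**Step 2 (8.4.4).** Up to approximately 30 patients are treated at the MTD found in Step 1.

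**Oversight (8.4.3.1).** The iDSMB confirms the MTD or the highest dose it judges tolerable. It may depart from the written escalation rule, recommend dose levels while the study runs, and meet whenever needed. For the expansion its listed task is: "Review safety data for additional patients recruited at the MTD or the maximum dose judged to be tolerable (at least every 2 months"). Its detailed responsibilities are left to a separate charter.

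**Size (9.1).** No formal calculation is made. The plan allows that "up to approximately 6 DLT evaluable patients per dose level will be treated with MEN1112 during the dose escalation phase", about 30 in expansion, 30% drop-out, and approximately 60 treated in total.

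**The concern.** The MTD is a primary endpoint and sets the Step 2 dose, yet it is defined entirely by what happens one level higher. A level passed on 0/3 is left with three evaluable patients, and nothing in the written rule sends the trial back to add three more when the next level fails.

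Three patients say little about the DLT rate at the dose chosen for expansion. Section 6.2.4.2 shows that DLTs in the one-shot part were not confined to the level that became the MAD: six patients met the DLT definition in all, and two of them were at 2.5 mg/kg. The one-shot patients at 1.7 mg/kg cannot stand in for a ramp-up cohort, because the schedule differs.

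In Step 2 a DLT ends that patient's treatment (8.2.3), but no stated number of DLTs pauses enrolment or reopens the MTD.

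**Working it through.** **1. The plan's own figure.** Four levels × 6 = 24 evaluable. Adding 30% gives 24 × 1.3 = 31.2, so 32, and 32 + 30 = 62. If instead the six patients at the MTD count towards the 30, then 24/0.7 = 34.3, so 35, and 35 + 24 = 59. Both agree with approximately 60. (24/0.7 with the full 30 gives 65.) Six evaluable patients at every level therefore already fit the planned maximum.

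**2. What the data at the MTD can exclude.** The exact two-sided 95% upper limit U solves P(X ≤ x | n, U) = 0.025. For x = 0 this is U = 1 − 0.025^(1/n).
- 0/3: 1 − 0.025^(1/3) = 1 − 0.292 = 70.8%
- 0/6: 1 − 0.025^(1/6) = 1 − 0.541 = 45.9%
- 1/6: (1 − U)^6 + 6U(1 − U)^5 = 0.025 gives U = 64.1%

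**3. Chance of accepting a level.** The documents give no target DLT rate, so the true rate p is assumed.
- A = (1 − p)^3: cleared on 0/3
- B = (1 − p)^3 + 3p(1 − p)^2: at most 1 DLT in three further patients
- A × B: cleared on 0/3 and still accepted at six
- Whole rule now: A + 3p(1 − p)^5, that is, 0/3, or 1/3 followed by 0/3
- Whole rule with six required: at most 1 DLT in 6

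| p | A | B | A × B | Rule now | At most 1/6 |
|---|---|---|---|---|---|
| 20% | 51.2% | 89.6% | 45.9% | 70.9% | 65.5% |
| 30% | 34.3% | 78.4% | 26.9% | 49.4% | 42.0% |
| 40% | 21.6% | 64.8% | 14.0% | 30.9% | 23.3% |
| 50% | 12.5% | 50.0% | 6.3% | 17.2% | 10.9% |

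At 30 to 50% the reduction is 6 to 8 percentage points. At 20% about 5 points of acceptance are lost.

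**4. How often the MTD would rest on three patients.** At one level, the share of passes that come through 0/3 is A divided by the current pass probability: 0.343/0.494 = 69% at p = 30% and 0.125/0.172 = 73% at 50%. The written rule was also followed exactly through the four ramp-up levels, with no intermediate levels and no iDSMB adjustment, under four assumed sets of DLT rates:

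| Assumed DLT rates at the four levels | Declared MTDs resting on 3 patients |
|---|---|
| 5/10/20/35% | 77% |
| 10/20/30/45% | 74% |
| 10/15/30/50% | 74% |
| 15/25/40/60% | 72% |

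**5. Patients treated to obtain three evaluable.** With 30% drop-out: 3 × 1.3 = 3.9, or 3/0.7 = 4.3, so four or five. Table 1 gives a similar answer from the one-shot part: 34 of 47 treated patients (72.3%) were in the DLT population, and 3/0.723 = 4.1.

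**The case against.** The strongest reply is that the iDSMB already covers this. It must confirm the MTD, may make adjustments, may recommend dose levels during the study, and can meet at any time, so two months is the longest interval between reviews and not the only trigger. Section 11 also lets the sponsor stop the trial for unexpectedly severe or frequent events. A reader might infer that nothing in Step 2 could revise the MTD, or that a 0/3 level can never be taken to six. The documents do not support either. The iDSMB has the discretion, intermediate levels may be explored, and the earlier 0.3 mg/kg cohort was taken to six without waiting for a DLT, although as a named exception. What remains is that these powers are discretionary and the protocol attaches no number to them. The charter may do so, but it is not available here.

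A reader might also infer from 9.1 that six patients per level were promised and then not used. The wording is a ceiling and is consistent with filling a level only after a DLT. It shows that six are affordable, not that they are owed.

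Finally, the benefit should not be judged by 0/3 against 0/6 alone. A six-patient rule also accepts 1/6, whose upper limit of 64% is not far below 71%. Six patients still describe the DLT rate poorly. This objection stands and limits the claim to a modest gain.

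**Conclusion.** The point holds as a gap in the written rule. The plan allows an MTD based on 0 DLTs in 3, and under the assumed curves that is the usual result of following the text, at 72 to 77% of declared MTDs. Requiring six evaluable patients lowers acceptance through 0/3 from 34/22/12.5% to 27/14/6% at true rates of 30/40/50%.

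These are chances of passing one level. They are not the chance that the level becomes the MTD, which also needs the next level to be the MAD. All DLT rates here are assumptions.

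The rule is explicit and consistent across 8.4.3, 8.5.4.1 and the synopsis, so this is an improvement to a workable design and not an internal contradiction. It is worth making because the gain, though small, comes within the planned patient numbers and replaces discretion with a stated criterion for a primary endpoint.

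**What to change.** In 8.4.3, and in the matching endpoint text of 8.5.4.1 and the synopsis, state that a level is confirmed as the MTD only when at least six DLT-evaluable patients have been treated there with at most one having a DLT.

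In 8.4.4, state that if the level was cleared on 0/3, the first three DLT-evaluable Step 2 patients count as patients four to six. Non-evaluable patients among them are replaced; 9.1 at present provides for replacement only in dose escalation. The iDSMB then applies the existing rule of two or more DLTs before the rest of Step 2 enrols. If the charter already holds such a rule, bring it into the protocol or cite it there.

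**Cost.** About four or five patients are treated to obtain three evaluable, within the Step 2 allotment and the six-per-level ceiling, with a pause of at least one 21-day cycle. That is the best case. If the level fails, those Step 2 patients have been used at a dose that is not carried forward, and the level below may also have to be filled to six, which lengthens the pause. No ramp-up level is listed below 1.7 mg/kg, so the protocol should also say how the iDSMB proceeds if that level fails.

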8.4.3.1 Dose-level escalation assessment

In place of the Cohort Review Committee (CRC), which was appointed to guide dose escalation decisions up to Protocol Version 4.1, starting from Protocol Version 6.1/6.2, the decision as to whether, or how, to proceed through the dose levels during Step 1 are guided by the iDMSB which will be comprised of independent AML experts.

The iDSMB will meet by telephone to review the latest safety, PK and Pharmacodynamics (PD) (if any) data prior to dose-escalation to a subsequent cohort, and at any time if needed. Appropriate representatives of the Sponsor and the coordinating CRO will also attend and minute the meeting. Decisions of the iDMSB will be documented and sent to the sites.

The iDSMB is empowered to:

• Review the safety data from the first cycle of each cohort during the dose escalation phase of the study and make dose-escalation (or de-escalation) decisions according to the protocol or making adjustments, as needed. AEs occurring in Cycle 2 which meet the definition of a DLT or are considered clinically significant may also be considered in making dose escalation decisions.

- Consider other AEs, or possible trends in AEs, during the dose escalation phase which may provide relevant information for the dose escalation.
- Confirm the MTD or the maximum dose judged to be tolerable for evaluation in Step 2.
- Review safety data for additional patients recruited at the MTD or the maximum dose judged to be tolerable (at least every 2 months).
- Recommend future dose level and dose schedule administration during the study conduct; advise on premedication, concomitant medication and on any individual patient dose adjustments.

Roles and responsibilities of iDSMB as well as meeting schedule and format of information will be set forth in a separate iDSMB Charter prior to start administrating the drug to the first patient under protocol version 6.1/6.2.

8.4.4 Step 2- Cohort expansion

Under Protocol Version 4.1, two patients experienced DLTs at the dose level of 2.5 mg/kg using the *"one-shot"* schedule of administration in Cycle 1. Therefore, the 1.7 mg/kg dose level was defined as the maximum tolerated dose (MTD) for the schedule of administration encompassing the *"one-shot"* infusion since Cycle 1; as a consequence, the expansion phase was opened to enrol up to 25 patients with MEN1112 given as *"one-shot"* infusions since Cycle 1.

Starting from protocol version 6.1/6.2, up to approximately 30 patients will be treated with MEN1112 given at the MTD identified in Step 1 using the modified schedule of treatment, i.e. encompassing the *"ramp-up"* approach during Cycle 1. In place of the CRC, which was appointed to assess the data collected during Step 2 up to Protocol Version 4.1, under Protocol Version 6.1/6.2 and following amendments the iDMSB, already implemented in Step 1 will be appointed also to assess the data collected during the Step 2 of the study.

8.4.5 Treatment regimen and duration

MEN1112 is to be administered intravenously for two treatment cycles.

Up to Protocol Version 4.1, MEN1112 was administered by intravenous "one-shot" weekly infusions for two 21-day cycles, followed by "one-shot" monthly infusions in patients demonstrating clinical benefit (as per Investigator's judgement) as long as such benefit was maintained. Starting from protocol version 6.1/6.2, MEN1112 will be administered for two 21-day cycles; the first two infusions of Cycle 1 will be given using a "3-day ramp-up" schedule of administration, i.e. the complete MEN1112 dose will be split in three days. Starting from the third infusion of Cycle 1 onwards, MEN1112 will be administered as "one-shot" infusions. The treatment plan by dose level will be therefore as following:

DOSE LEVEL	CYCLE 1	CYCLE 2
1.7 mg/kg	Visit 1/Day 1: 0.1 mg/kg	Visit 16/Day 22: 1.7 mg/kg
	Visit 2/Day 2: 0.6 mg/kg	Visit 20/Day 29: 1.7 mg/kg
	Visit 3/Day 3: 1.0 mg/kg	Visit 24/Day 36: 1.7 mg/kg
	Visit 8/Day 8: 0.1 mg/kg	
	Visit 9/Day 9: 0.6 mg/kg	
	Visit 10/Day 10: 1.0 mg/kg	
	Visit 12/Day 15: 1.7 mg/kg	
2.0 mg/kg	Visit 1/Day 1: 0.1 mg/kg	Visit 16/Day 22: 2.0 mg/kg
	Visit 2/Day 2: 0.7 mg/kg	Visit 20/Day 29: 2.0 mg/kg
	Visit 3/Day 3: 1.2 mg/kg	Visit 24/Day 36: 2.0 mg/kg
	Visit 8/Day 8: 0.1 mg/kg	
	Visit 9/Day 9: 0.7 mg/kg	
	Visit 10/Day 10: 1.2 mg/kg	
	Visit 12/Day 15: 2.0 mg/kg	
3.0 mg/kg	Visit 1/Day 1: 0.2 mg/kg	Visit 16/Day 22: 3.0 mg/kg
3.0 mg/kg	Visit 1/Day 1: 0.2 mg/kg Visit 2/Day 2: 1.0 mg/kg	Visit 16/Day 22: 3.0 mg/kg Visit 20/Day 29: 3.0 mg/kg
3.0 mg/kg	Visit 1/Day 1: 0.2 mg/kg Visit 2/Day 2: 1.0 mg/kg Visit 3/Day 3: 1.8 mg/kg	Visit 16/Day 22: 3.0 mg/kg Visit 20/Day 29: 3.0 mg/kg Visit 24/Day 36: 3.0 mg/kg
3.0 mg/kg	Visit 1/Day 1: 0.2 mg/kg Visit 2/Day 2: 1.0 mg/kg Visit 3/Day 3: 1.8 mg/kg Visit 8/Day 8: 0.2 mg/kg	Visit 16/Day 22: 3.0 mg/kg Visit 20/Day 29: 3.0 mg/kg Visit 24/Day 36: 3.0 mg/kg
3.0 mg/kg	Visit 1/Day 1: 0.2 mg/kg Visit 2/Day 2: 1.0 mg/kg Visit 3/Day 3: 1.8 mg/kg Visit 8/Day 8: 0.2 mg/kg Visit 9/Day 9: 1.0 mg/kg	Visit 16/Day 22: 3.0 mg/kg Visit 20/Day 29: 3.0 mg/kg Visit 24/Day 36: 3.0 mg/kg
3.0 mg/kg	Visit 1/Day 1: 0.2 mg/kg Visit 2/Day 2: 1.0 mg/kg Visit 3/Day 3: 1.8 mg/kg Visit 8/Day 8: 0.2 mg/kg Visit 9/Day 9: 1.0 mg/kg Visit 10/Day 10: 1.8 mg/kg	Visit 16/Day 22: 3.0 mg/kg Visit 20/Day 29: 3.0 mg/kg Visit 24/Day 36: 3.0 mg/kg
3.0 mg/kg	Visit 1/Day 1: 0.2 mg/kg Visit 2/Day 2: 1.0 mg/kg Visit 3/Day 3: 1.8 mg/kg Visit 8/Day 8: 0.2 mg/kg Visit 9/Day 9: 1.0 mg/kg Visit 10/Day 10: 1.8 mg/kg Visit 12/Day 15: 3.0 mg/kg	Visit 16/Day 22: 3.0 mg/kg Visit 20/Day 29: 3.0 mg/kg Visit 24/Day 36: 3.0 mg/kg
3.0 mg/kg 5.0 mg/kg	Visit 1/Day 1: 0.2 mg/kg Visit 2/Day 2: 1.0 mg/kg Visit 3/Day 3: 1.8 mg/kg Visit 8/Day 8: 0.2 mg/kg Visit 9/Day 9: 1.0 mg/kg Visit 10/Day 10: 1.8 mg/kg Visit 12/Day 15: 3.0 mg/kg Visit 1/Day 1: 0.3 mg/kg	Visit 16/Day 22: 3.0 mg/kg Visit 20/Day 29: 3.0 mg/kg Visit 24/Day 36: 3.0 mg/kg Visit 16/ Day 22: 5.0 mg/kg
3.0 mg/kg 5.0 mg/kg	Visit 1/Day 1: 0.2 mg/kg Visit 2/Day 2: 1.0 mg/kg Visit 3/Day 3: 1.8 mg/kg Visit 8/Day 8: 0.2 mg/kg Visit 9/Day 9: 1.0 mg/kg Visit 10/Day 10: 1.8 mg/kg Visit 12/Day 15: 3.0 mg/kg Visit 1/Day 1: 0.3 mg/kg Visit 2/Day 2: 1.7 mg/kg	Visit 16/Day 22: 3.0 mg/kg Visit 20/Day 29: 3.0 mg/kg Visit 24/Day 36: 3.0 mg/kg Visit 16/ Day 22: 5.0 mg/kg Visit 20/ Day 29: 5.0 mg/kg
3.0 mg/kg 5.0 mg/kg	Visit 1/Day 1: 0.2 mg/kg Visit 2/Day 2: 1.0 mg/kg Visit 3/Day 3: 1.8 mg/kg Visit 8/Day 8: 0.2 mg/kg Visit 9/Day 9: 1.0 mg/kg Visit 10/Day 10: 1.8 mg/kg Visit 12/Day 15: 3.0 mg/kg Visit 1/Day 1: 0.3 mg/kg Visit 2/Day 2: 1.7 mg/kg Visit 3/Day 3: 3.0 mg/kg	Visit 16/Day 22: 3.0 mg/kg Visit 20/Day 29: 3.0 mg/kg Visit 24/Day 36: 3.0 mg/kg Visit 16/ Day 22: 5.0 mg/kg Visit 20/ Day 29: 5.0 mg/kg Visit 24/ Day 36: 5.0 mg/kg
3.0 mg/kg 5.0 mg/kg	Visit 1/Day 1: 0.2 mg/kg Visit 2/Day 2: 1.0 mg/kg Visit 3/Day 3: 1.8 mg/kg Visit 8/Day 8: 0.2 mg/kg Visit 9/Day 9: 1.0 mg/kg Visit 10/Day 10: 1.8 mg/kg Visit 10/Day 15: 3.0 mg/kg Visit 1/Day 1: 0.3 mg/kg Visit 2/Day 2: 1.7 mg/kg Visit 3/Day 3: 3.0 mg/kg Visit 3/Day 8: 0.3 mg/kg	Visit 16/Day 22: 3.0 mg/kg Visit 20/Day 29: 3.0 mg/kg Visit 24/Day 36: 3.0 mg/kg Visit 16/ Day 22: 5.0 mg/kg Visit 20/ Day 29: 5.0 mg/kg Visit 24/ Day 36: 5.0 mg/kg
3.0 mg/kg 5.0 mg/kg	Visit 1/Day 1: 0.2 mg/kg Visit 2/Day 2: 1.0 mg/kg Visit 3/Day 3: 1.8 mg/kg Visit 8/Day 8: 0.2 mg/kg Visit 9/Day 9: 1.0 mg/kg Visit 10/Day 10: 1.8 mg/kg Visit 12/Day 15: 3.0 mg/kg Visit 1/Day 1: 0.3 mg/kg Visit 2/Day 2: 1.7 mg/kg Visit 3/Day 3: 3.0 mg/kg Visit 8/Day 8: 0.3 mg/kg Visit 9/Day 9: 1.7 mg/kg	Visit 16/Day 22: 3.0 mg/kg Visit 20/Day 29: 3.0 mg/kg Visit 24/Day 36: 3.0 mg/kg Visit 16/ Day 22: 5.0 mg/kg Visit 20/ Day 29: 5.0 mg/kg Visit 24/ Day 36: 5.0 mg/kg
3.0 mg/kg 5.0 mg/kg	Visit 1/Day 1: 0.2 mg/kg Visit 2/Day 2: 1.0 mg/kg Visit 3/Day 3: 1.8 mg/kg Visit 8/Day 8: 0.2 mg/kg Visit 9/Day 9: 1.0 mg/kg Visit 10/Day 10: 1.8 mg/kg Visit 10/Day 10: 1.8 mg/kg Visit 1/Day 1: 0.3 mg/kg Visit 2/Day 2: 1.7 mg/kg Visit 2/Day 3: 3.0 mg/kg Visit 8/Day 8: 0.3 mg/kg Visit 9/Day 9: 1.7 mg/kg Visit 9/Day 9: 1.7 mg/kg Visit 10/Day 10:3.0 mg/kg	Visit 16/Day 22: 3.0 mg/kg Visit 20/Day 29: 3.0 mg/kg Visit 24/Day 36: 3.0 mg/kg Visit 16/ Day 22: 5.0 mg/kg Visit 20/ Day 29: 5.0 mg/kg Visit 24/ Day 36: 5.0 mg/kg

During Cycle 1, patients must be treated and monitored in-hospital up to at least 24 hours after each study drug administration visit.

Confidential Menarini Ricerche S.p.A.

The total dose calculated for the first study drug administration can be applied also for the following ones providing that actual patient's weight is within $\pm 10\%$ of the weight measured prior to the first study drug administration. Otherwise, the total dose to be given shall be calculated based on the weight measured at the corresponding visit.

The individual study period (including the follow-up) is six months (except for female patients of childbearing potential, who will be required to undergo a monthly pregnancy test until 6 months from the last study drug administration).

